7.9 Changes From Protocol

The interim analysis described in section 7.7 was not included in the protocol.

8. Transfer of documentation, data and reporting

Data, documentation and reporting will be shared between the Study team, CTRU, SSU and Pfizer as detailed below. The transfers will use a mutually agreeable electronic transmission method that is demonstrated to be compatible with uploading to the targeted Pfizer database or Pfizer systems and that protects the security and integrity of the data. All deliverables provided to Pfizer will be written in English.

Documentation

- Monthly status reports will be provided to Pfizer by **the study team** in Excel Format, SAS Format, or XPT Format to include:
 - monthly updates of first participant first visit, participant screened, and randomized to date, screen failures to date
 - Participants completed; and
 - any other information as may reasonably be requested by Pfizer
- At the time of study reporting **the SSU** will provide listings (pdf document) by Study subject, for all enrolled Study subjects (not including screen failures) for the following variables as a minimum:
 - subject no.,
 - enrollment date,
 - randomization date,
 - dosing date
- The **study team** will provide the follow documents to Pfizer and the SSU in the form of one or more Portable Document Format (“**PDF**”) files and as they become available:
 - annotated CRFs
 - an electronic “Data Dictionary” consisting of all versions of the CRFs used in the Study, annotated with variable names and corresponding datasets
 - documentation of dictionary coding versions used to code medications and SAEs/AEs
 - Any derivations used at the point of data entry or during data cleaning
 - TMF-associated documentation, including, but not limited to:
 - , blank/template CRF,
 - CRF approval(s),
 - clinical data change report,
 - all versions of CRF completion guidelines,
 - completed CRFs,
 - database entry and database user acceptance testing documentation,
 - data management plan(s) (inclusive of edit checks),

- data review plan(s) and database release documentation,
- any other documentation as may reasonably be requested by Pfizer

- The **SSU** will provide SAP for review and at sign off (plus if any amendments are required)
 - Any derivations used for the analysis will be included in the SAP/added to an appendix of the SAP as appropriate
 - relevant statistical analysis assumptions or plans will be included in the SAP/added to an appendix of the SAP as appropriate

Clinical Datasets

A “**Clinical Dataset**” consists of all Study Data (with certain personal identifiers removed) available to Trust at the time of transfer. Clinical Datasets may include raw datasets and/or analysis datasets. Trust will transfer Clinical Datasets and in the form of SAS Export/Transport file format (XPT) files or CSV files as detailed below.

Test transfers

Prior to transfer of a given Clinical Dataset to Pfizer, **the study team** will transfer test data to support the effective transfer of such Clinical Dataset. A test data set will consist of complete “dummy” data for at least 5 hypothetical or actual Study subjects. Pfizer will perform certain checks on test data to determine if the transmission meets Pfizer requirements in content and process and if the data will load successfully into the target Pfizer database. Trust will work with Pfizer if changes are needed in the data formatting or transmission process to ensure data quality and usability. Trust will transfer additional sets of test data if needed after such changes are made, as well as if there are any changes in the Study variables or data collection tools during the Study. **Transfers from the study team will be of RAW data in csv format.**

When a test transfer is available it will be provided to the SSU by the **study team**.

Data transfers

The study team will transfer a Clinical Dataset to Pfizer: after fifteen (15) of subjects dosed and after study completion.

At the time of study reporting (when the final analysis is complete) the **SSU** will provide clinical datasets in SAS format. A test transfer can be done in advance, however, there may be small changes to variables up until the final analysis is agreed.

Data cleaning and validation

Pfizer, the study team and the SSU will alert each other promptly if they discover that any data within a Clinical Dataset fails to meet appropriate quality standards. This may include data queries from **Pfizer** or the **SSU** that **the study team** will investigate and resolve.

Results Summary

The **SSU** will provide tables and listings to the **study team** and **Pfizer** following the final analysis, the format of these will be agreed in advance and will include:

- subject population summaries
- efficacy results
- safety results
- the SSU will advise on statistical interpretation of primary results

In addition, the study team may provide commentary on the objectives and study design and clinical interpretation.

Timelines for the delivery of the tables and listings will be agreed between the study team, the SSU and Pfizer.

Study Report

- Whilst the **SSU** will input and advise with respect to the statistical design, methodology and interpretation the **study team** will be responsible for writing the study report.
- A draft of the written Study Report will be delivered to Pfizer in accordance with the information and formatting as agreed to by **the study team** and in accordance with ICH-E3 guidelines. The Study Report will reflect the results of the Study as a whole. **Study team** will provide Pfizer with an opportunity to review and comment on the draft Study Report for at least thirty (30) days after Pfizer's receipt of the draft Study Report, and Trust and Principal Investigator will consider in good faith any comments reasonably
- Within five (5) months after the last subject's last visit or database lock or upon early termination of the study, whichever occurs first, **the study team** will provide Pfizer with the final Study Report. In case of early termination of the study (before Study Completion), the Study Report will include, at minimum, the Study Results through the date of termination. Unless otherwise agreed in writing, The Trust may submit the Study Report to applicable regulatory authorities.
- Unless otherwise agreed by Pfizer, the Study Report will address:
 - Ethics
 - Investigators and Study administration
 - Study objectives
 - investigational plan
 - Study subjects
 - efficacy evaluation
 - Drug compliance/adherence evaluation
 - safety evaluation
 - discussion and overall conclusions; supportive tables, figures and graphs;
 - biomarker findings; and
 - any other information as may reasonably be requested by Pfizer.

9. List of Tables, Figures and Listings

Tables

14.1.1 Disposition (Full Analysis Set)
14.1.2 Important PDs (Full Analysis Set)
14.1.3 Patients excluded from analysis populations (Full Analysis Set)
14.1.4 Demographic data (Full Analysis Set)
14.1.5 Baseline eczema history (Full Analysis Set)
14.1.6 Medical History (Full Analysis Set)
14.1.7 Temperature and humidity during skin assessments (Full Analysis Set)
14.2.1 Epidermal thickness. (Full Analysis Set)
14.2.1.1 Change in epidermal thickness during and after 4 weeks of treatment (day 15 – day 1, day 29 – day 1, day 57 – day 1) (Full Analysis Set)
14.2.1.2 Analysis of epidermal thickness change (day 15 – day 1, day 29 – day 1, day 57 – day 1) (Full Analysis Set)
Note for this table and similar tables for the secondary endpoints – only those comparisons carried out will be included – see section 7.2
14.2.2 TEWL (g/m²h) (Full Analysis Set)
14.2.2.1 Change in TEWL (g/m²h) during and after 4 weeks of treatment (day 15 – day 1, day 29 – day 1, day 57 – day 1) (Full Analysis Set)
14.2.2.2 Analysis of change in TEWL (day 15 – day 1, day 29 – day 1, day 57 – day 1) (Full Analysis Set)
14.2.3 TEWL_{ts20} (g/m²h) (Full Analysis Set)
14.2.3.1 Change in TEWL_{ts20} (g/m²h) after 4 weeks of treatment (day 29) (Full Analysis Set)
14.2.3.2 Analysis of change in TEWL_{ts20} following 4 weeks of treatment (Full Analysis Set)
14.2.4 NMF (Full Analysis Set)
14.2.4.1 Analysis of NMF (day 29) (Full Analysis Set)
14.2.5 Investigator visual scores for redness (Full Analysis Set)
14.2.5.1 Change in visual score for redness during and after 4 weeks of treatment (day 15 – day 1, day 29 – day 1, day 57 – day 1) (Full Analysis Set)
14.2.5.2 Analysis of change in visual score for redness (day 15 – day 1, day 29 – day 1, day 57 – day 1) (Full Analysis Set)
14.2.6 Objective Redness (Mexameter) (Full Analysis Set)
14.2.6.1 Change in Objective Redness (Mexameter) during and after 4 weeks of treatment (day 15 – day 1, day 29 – day 1, day 57 – day 1) (Full Analysis Set)
14.2.6.2 Analysis of change in Objective Redness (Mexamater) (day 15 – day 1, day 29 – day 1, day 57 – day 1) (Full Analysis Set)
14.2.7 Dryness (Full Analysis Set)
14.2.7.1 Change in Dryness during and after 4 weeks of treatment (day 15 – day 1, day 29 – day 1, day 57 – day 1) (Full Analysis Set)
14.2.7.2 Analysis of change in dryness (day 15 – day 1, day 29 – day 1, day 57 – day 1) (Full Analysis Set)
14.2.8 Superficial plexus depth (μm) (Full Analysis Set)
14.2.8.1 Change from baseline in superficial plexus depth (μm) (day 15 – day 1, day 29 – day 1, day 57 – day 1) (Full Analysis Set)
14.2.9 Mean blood vessel diameter (μm) (Full Analysis Set)
14.2.9.1 Change from baseline in mean blood vessel diameter (μm) (day 15 – day 1, day 29 – day 1, day 57 – day 1) (Full Analysis Set)

14.2.10 Blood vessel density (segments/m²) (Full Analysis Set)
14.2.10.1 Change from baseline in blood vessel density (segments/m²) (day 15 – day 1, day 29 – day 1, day 57 – day 1) (Full Analysis Set)
14.2.11 Collagen matrix index (Full Analysis Set)
14.2.11.1 Change from baseline in collagen matrix index (day 15 – day 1, day 29 – day 1, day 57 – day 1) (Full Analysis Set)
14.2.12 Carboxylate levels (FTIR) (Full Analysis Set)
14.2.12.1 Change from baseline in carboxylate levels (FTIR – indirect NMF) (day 15 – day 1, day 29 – day 1, day 57 – day 1) (Full Analysis Set)
14.2.13 Stratum corneum lipid (Full Analysis Set)
14.2.13.1 Change from baseline in stratum corneum lipid (day 15 – day 1, day 29 – day 1, day 57 – day 1) (Full Analysis Set)
14.2.14 Summary of FLG (Full Analysis Set)
14.2.14.1 Summary of epidermal thickness by mutation status (Full Analysis Set)
14.2.14.1.1 Analysis of change in epidermal thickness (day 29 – day 1) within mutation status (Full Analysis Set)
14.2.14.2 Summary of TEWL (g/m²h) by mutation status (Full Analysis Set)
14.2.14.2.1 Analysis of change in TEWL (g/m²h) (day 15 – day 1, day 29 – day 1, day 57 – day 1) within mutation status (Full Analysis Set)
14.2.15 Total Product consumption (Safety Analysis Set)
14.3.1 Number of patients experiencing AEs (Safety Analysis Set)
14.3.2 Adverse Events by system organ class and preferred term (Safety Analysis Set)
14.3.x Adverse Events - further tables as appropriate (Safety Analysis Set)
BDR1.1 Summary of epidermal thickness by location (Full Analysis Set)
BDR1.2 Summary of epidermal thickness change by location (day 29 – day 1) (Full Analysis Set)
BDR1.3 Summary of epidermal thickness change after treatment cessation by location (day 57 – day 29) (Full Analysis Set)
BDR2.1 Summary of TEWL (g/m²h) by location (Full Analysis Set)
BDR2.2 Summary of TEWL (g/m²h) change by location (day 15 – day 1, day 29 – day 1, day 57 – day 1) (Full Analysis Set)
BDR3.1 Summary of TEWL_{ts20} (g/m²h) by location (Full Analysis Set)
BDR3.2 Summary of TEWL_{ts20} (g/m²h) change by location (day 29 – day 1)
BDR4.1 Summary of NMF by location (Full Analysis Set)
BDR4.2 Summary of NMF change by location (day 15 – day 1, day 29 – day 1, day 57 – day 1) (Full Analysis Set)
BDR5.1 Summary of visual scores for redness (erythema) by location (Full Analysis Set)
BDR5.2 Summary of visual scores for redness (erythema) change by location (day 15 – day 1, day 29 – day 1, day 57 – day 1) (Full Analysis Set)
BDR6.1 Summary of Objective redness (Mexameter) by location (Full Analysis Set)
BDR6.2 Summary of Objective redness (Mexameter) change by location (day 15 – day 1, day 29 – day 1, day 57 – day 1) (Full Analysis Set)
BDR7.1 Summary of Dryness by location (Full Analysis Set)
BDR7.2 Summary of Dryness change by location (day 15 – day 1, day 29 – day 1, day 57 – day 1) (Full Analysis Set)
BDR8.1 Summary of Superficial plexus depth (μm) by location (Full Analysis Set)
BDR8.2 Summary of Superficial plexus depth (μm) change by location (day 15 – day 1, day 29 – day 1, day 57 – day 1) (Full Analysis Set)
BDR9.1 Summary of Mean blood vessel diameter (μm) by location (Full Analysis Set)

BDR9.2	Summary of Mean blood vessel diameter (μm) change by location (day 15 – day 1, day 29 – day 1, day 57 – day 1) (Full Analysis Set)
BDR10.1	Summary of blood vessel density (segments/ m^2) by location (Full Analysis Set)
BDR10.2	Summary of blood vessel density (segments/ m^2) change by location (day 15 – day 1, day 29 – day 1, day 57 – day 1) (Full Analysis Set)
BDR11.1	Summary of collagen matrix index by location (Full Analysis Set)
BDR11.2	Summary of collagen matrix index change by location (day 15 – day 1, day 29 – day 1, day 57 – day 1) (Full Analysis Set)
BDR12.1	Summary of carboxylate levels (FTIR) by location (Full Analysis Set)
BDR12.2	Summary of carboxylate levels (FTIR) change by location (day 15 – day 1, day 29 – day 1, day 57 – day 1) (Full Analysis Set)
BDR13.1	Summary of stratum corneum lipid by location (Full Analysis Set)
BDR13.2	Summary of stratum corneum lipid change by location (day 15 – day 1, day 29 – day 1, day 57 – day 1) (Full Analysis Set)

Listings

16.2.1	Discontinued patients (All patients)
16.2.2	Protocol deviations (Full Analysis Set)
16.2.3	Patients excluded from analysis populations (All patients)
16.2.4.1	Demographic data (Full Analysis Set)
16.2.4.2	Baseline eczema history (Full Analysis Set)
16.2.4.3	Medical history (Full Analysis Set)
16.2.4.4	Patient routine (Full Analysis Set)
16.2.5	Cream consumption (Full Analysis Set)
16.2.6.1	Epidermal thickness (Full Analysis Set)
16.2.6.2	TEWL (Full Analysis Set)
16.2.6.3	Investigator visual scores for redness (Full Analysis Set)
16.2.6.4	Objective erythema (Full Analysis Set)
16.2.6.5	Objective Redness (Mexameter) (Full Analysis Set)
16.2.6.6	TEWL _{ts20} (Full Analysis Set)
16.2.6.7	Skin surface dryness (3D skin images) (day 29 – day 1) (Full Analysis Set)
16.2.6.8	Superficial plexus depth (Full Analysis Set)
16.2.6.9	Blood vessel diameter (Full Analysis Set)
16.2.6.10	Blood vessel density (Full Analysis Set)
16.2.6.11	Collagen matrix index (Full Analysis Set)
16.2.6.12	Carboxylate levels (Full Analysis Set)
16.2.6.13	Stratum corneum lipid (Full Analysis Set)
16.2.6.14	TEWL _{ts5} (Full Analysis Set)
16.2.6.14	TEWL _{ts10} (Full Analysis Set)
16.2.6.14	TEWL _{ts15} (Full Analysis Set)
16.2.6.15	Patient tolerability scores (VAS) (Full Analysis Set)
16.2.6.16	Total Cream consumption (Full Analysis Set)
16.2.6.17	NMF (Full Analysis Set)
16.2.6.18	FLG (Full Analysis Set)
16.2.7	AEs (Safety Analysis Set)

Figures:

Figure 14.2.1.1 Epidermal thickness by visit (day 1, day 15, day 29, day 57) (Full Analysis Set)
Figure 14.2.2.1 Erythema (visual redness) by visit (day 1, day 15, day 29, day 57) (Full Analysis Set)
Figure 14.2.3.1 Objective redness (mexameter) (day 1, day 15, day 29, day 57) (Full Analysis Set)
Figure 14.2.4.1 TEWL (g.m⁻²h) by visit (day 1, day 15, day 29, day 57) (Full Analysis Set)
Figure 14.2.7.1 Skin surface dryness (μm) (day 1, day 15, day 29, day 57) (Full Analysis Set)
Figure 14.2.8.1 NMF levels at day 29(Full Analysis Set)
Figure 14.2.9.1 Superficial plexus depth (μm) (day 1, day 15, day 29, day 57) (Full Analysis Set)
Figure 14.2.10.1 Mean blood vessel diameter (μm) (day 1, day 15, day 29, day 57) (Full Analysis Set)
Figure 14.2.11.1 Blood vessel density (segments/mm²) (day 1, day 15, day 29, day 57) (Full Analysis Set)
Figure 14.2.12.1 Collagen matrix index (day 1, day 29) (Full Analysis Set)
Figure 14.2.13.1 Carboxylate levels (day 1, day 15, day 29, day 57) (Full Analysis Set)
Figure 14.2.14.1 Stratum corneum lipid structure (day 29) (Full Analysis Set)
Figure 14.2.15.1 Epidermal thickness split by FLG mutation (day 1, day 15, day 29, day 57) (Full Analysis Set)
Figure 14.2.16.1 TEWL split by FLG mutation (day 1, day 15, day 29, day 57) (Full Analysis Set)

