Informed consent will not be retaken where the participant is returning after a defined/scheduled washout period of up to 16 weeks (12 weeks + 28 days). Volunteers who reapply to take part after this time or where a washout period was not scheduled (and documented in the admission form), will be required to re-consent.

Where the participant meets all of the eligibility criteria at the screening visit, Visit 1/baseline may be arranged within 28 days without the need to repeat the admission process. If more than 28 days lapses before the participant can attend visit 1 the admission process should be completed to ensure the participant is still eligible and that the background information is still valid (this will involve completing a follow-up admission form). Visit 1 may also be combined with the screening visit (same day) IF the participant is found to be eligible without the need for a washout period.

The Participant Screening, Enrolment & Completion Log will be completed and all screened participants assigned a unique study screening number.

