9.2 Reporting Period

The reporting period for adverse events will be from the date of informed consent until approximately 28 days after the last administration of IMP (range from 25 days to 36 days follow-up). All AE's will be followed up until causality has been assigned. Once causality has been assigned, only SAEs that are ongoing at the close of the reporting period will be followed up by the study team until they are either resolved or stabilised with properly assessed expectedness assessment for those SAEs which are considered causally related.

For participants who are screen failures, the active collection period ends when screen failure status is determined.

Investigators are not obligated to actively seek AEs or SAEs after conclusion of the study participation. However, if the investigator learns of any SAE, including a death, at any time after a participant has been discharged from the study, and he/she considers the event to be reasonably related to the study intervention or study participation, the investigator must promptly notify the sponsor.

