10.4.1 Summary of baseline data and flow of patients

Relevant baseline and demographic data (including Fitzpatrick skin type) will be summarised.

Treatment emergent adverse events and serious adverse events will be summarised for all participants who signed the consent. All adverse events will be listed (including those which began before initiation of study treatment or after the follow up period).

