To investigate whether OCT-derived biomarkers (other than the established structural OCT biomarker) enable the accurate quantification of tissue changes (vascular and matrix) associated with epidermal atrophy in response to TCS treatment. Biomarker measurements from the images will include:

- Superficial plexus depth (μm) from angiographic OCT images
- Mean vessel diameter (μm) from angiographic OCT images
- Vessel density (segments/ mm^2) from angiographic OCT images
- Collagen matrix index from polarisation sensitive OCT images

To investigate whether FTIR spectroscopy-derived biomarkers enable the accurate quantification of skin barrier condition and function in response to TCS treatment. Biomarker measurements from the spectra will include:

- NMF levels in the skin
- Lipid Structure

To investigate the number of participants with FLG loss-of-function mutations and explore if there is any evidence of a relationship to treatment effects.

To identify (by completing the objectives above) a panel of biomarkers that best characterises epidermal atrophy.

5. Analysis Sets and Protocol Deviations

Full Analysis Set (FAS): All subjects who were randomised into the study.

Per-protocol set (PPS): All participants who are deemed to have no major protocol violations that could interfere with the objectives of this study. This is a sub-population of the FAS.

Safety set: All randomised participants who receive at least 1 dose of test or reference cream.

All efficacy analyses and summaries will be performed on the FAS. If there are concerns about protocol deviations at the blind review, then a sensitivity analysis of the primary objective may be performed on the PPS.

Safety summaries will be performed on the safety set.

Prior to unblinding, a blind review of the data will be performed. The objective of the review is to identify protocol deviations and data queries and to make decisions regarding data analytical issues under blind conditions. Important violations of eligibility criteria and other deviations from the protocol will be assessed in cooperation with the study team. Important deviations from the protocol may lead to exclusion of a participant from the PPS. All deviations will be discussed and agreed prior to the unblinding of the data.

6. Endpoints and Covariates

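### The SAP limits every AE table and its only AE listing to dosed participants, while the protocol lists all AEs and summarises over everyone who signed consent, and the SAP does not declare the change

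*SAP*

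**What the plan says.** **Protocol.** Section 9.2: "The reporting period for adverse events will be from the date of informed consent". The same section continues active collection in screen failures until that status is determined. Section 10.4.1 makes two reporting commitments. Its first sentence names treatment-emergent adverse events and then continues: "serious adverse events will be summarised for all participants who signed the consent". Its second sentence is: "All adverse events will be listed (including those which began before initiation of study treatment". It also covers events after follow-up.

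**SAP.** Section 5 defines the Safety Set as "All randomised participants who receive at least 1 dose of test or reference cream" and runs safety summaries on it. In section 9, Table 14.3.1 is "Number of patients experiencing AEs (Safety Analysis Set"; Tables 14.3.2 and 14.3.x carry the same label, as does Listing 16.2.7, "AEs (Safety Analysis Set". There is no other AE listing. Section 7.4 instead summarises AEs for enrolled subjects. Section 8, describing a different listing, uses that word as follows: "for all enrolled Study subjects (not including screen failures". Section 7.9 declares one change from the protocol, the interim analysis.

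**The concern.** The two documents report AEs for different people. The protocol starts from consent and the SAP starts from the first dose. The gap matters in this trial because some participants must stop eczema treatment after consent and before Visit 1. Protocol 7.4.2 gives washouts from 7 days for emollients to 12 weeks for biologics. An untoward event in that interval is linked to a procedure that the trial requires. If the person is then not randomised and dosed, no planned output shows the event.

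What is at stake is the completeness of the safety record for the period between consent and treatment, and an undeclared departure from a protocol commitment. The primary endpoint and the comparison of the two products are not at stake.

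**Working it through.** The point rests on no sample size, power or error rate, so the check is a comparison of populations.

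**Step 1. Who is covered, by group.**

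| Group | AEs collected (Protocol 9.2) | All-AE listing (Protocol 10.4.1) | SAP 5 and 9 | SAP 7.4 |
|---|---|---|---|---|
| Consented, screen failure | Yes, until status is determined | Yes | No | No |
| Randomised, no dose | Yes, from consent | Yes | No | Yes |
| Randomised, at least one dose | Yes | Yes | Yes | Yes |

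The first two rows are the gap. The second should be nearly empty, because randomisation and the first supervised application both fall on Visit 1. It does show that SAP 7.4 disagrees with SAP 5 and 9.

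**Step 2. Does enrolment in SAP 7.4 include screen failures?** No. Protocol 7.5 makes allocation of the randomisation number the point of entry to the trial. Protocol 7.10.2 speaks of people who signed consent but are not enrolled. SAP 8 states that its listing of enrolled subjects leaves screen failures out.

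**Step 3. Which protocol commitments are affected?**
- *All-AE listing:* clearly affected. Section 10.4.1 puts no dosing condition on it.
- *Treatment-emergent AE summary:* not affected, because an undosed person cannot have a treatment-emergent event.
- *SAE summary:* affected if treatment-emergent qualifies only the first noun in the sentence, and not affected if it qualifies both. The sentence allows either reading.

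**Step 4. Are the data available?** Yes. The schedule of events (Protocol Table 7.1) captures AEs on the AE Form at screening and at Visit 1, and Protocol 9.3 records all AEs in a CRF. SAP 6.4 describes AEs as coming from participant diaries, which are issued only at Visit 1 (Protocol 7.4.3). A listing built from diaries alone would miss events before Visit 1, even in people who are later dosed.

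**Step 5. How many people?** The documents give no screen-failure rate. To show scale only, assume that a share s of consented people fail screening and 37 are randomised. The number outside every AE output is then 37/(1 − s), rounded up, minus 37:
- s = 10%: 42 − 37 = 5
- s = 30%: 53 − 37 = 16
- s = 50%: 74 − 37 = 37

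These counts include people who fail at the consent visit with no washout and no event. They do not estimate how many AEs are omitted.

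**The case against.** **Such events are not lost.** They are recorded in a CRF (Protocol 9.3). SAEs go to the sponsor and the funder on expedited timelines with no condition on dosing (9.3.1, 9.4). The reason for non-enrolment is logged for anyone who signed consent (7.10.2), and the final report must describe adverse events (14.2). This stands. A reader might infer that these events are reported nowhere, and the documents do not support that. None of these routes is a SAP table or listing, though, and non-serious events have no other planned tabulation.

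**The protocol is not uniform.** Section 9.1 defines an AE in someone who has been given a medicinal product, which would fit a dosed-only set. But 9.2 expressly collects AEs in screen failures, and 9.3 defines an AE as any untoward occurrence during the trial. The tension is real and does not remove the commitment in 10.4.1.

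**Safety sets normally require dosing.** That is right for treatment-emergent and product tables, and no change is proposed there. Washout events in people who are later dosed are also not excluded by the population rule, which concerns who is counted rather than when an event began.

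**The omission is selective.** A reader might infer that people harmed by washout are the ones most likely never to be dosed. The documents do not establish this. A forearm ISGA score of 1, the almost-clear grade, is enough to exclude (exclusion criterion 3). Relapse as an adverse event is defined by escalation of treatment (7.10.2), and a pre-existing condition counts as an AE only on significant worsening (9.3). Someone can be excluded without any AE.

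**The interval is very long.** Protocol 7.3 allows return without re-consent after "a defined/scheduled washout period of up to 16 weeks (12 weeks + 28 days", which is 16 × 7 = 112 days. That is an outer limit. The 12-week washout applies to biologics; other classes need 7 to 28 days (8.8.1), and screening may fall on the same day as Visit 1. Comparing 112 days with the 56 days from Day 1 to Day 57 would mislead.

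**Conclusion.** The SAP as written conflicts with the protocol on whose AEs are reported, and the difference is undeclared. AEs in consented but undosed participants, including any during a required washout, appear in no planned SAP table or listing. The clear loss is from the all-AE listing; the loss from the SAE summary depends on how one sentence in 10.4.1 is read.

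The conclusion rests on two readings: that the listing of all AEs in 10.4.1 includes those that 9.2 collects in screen failures, and that enrolment means randomisation. Both are supported by the text. The number of people or events affected cannot be determined from the documents. Expedited safety oversight, the primary result and the product comparison are unaffected, so this is a correction worth making before database lock and not a threat to the trial's main conclusion.

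**What to change.** - Define in SAP 5 a population of all participants who signed consent. Do not rely on the *All patients* label of Listings 16.2.1 and 16.2.3, which the SAP never defines.
- Set Listing 16.2.7 to that population, with a dosed/not-dosed flag, and draw it from the AE Form as well as the diary.
- Add to Table 14.3.1 the number of consented but undosed participants with any AE and with any SAE.
- Keep treatment-emergent and product-comparison tables on the Safety Set.
- Align SAP 5, 7.4 and 9 (and the AE source in 6.4), and record any remaining difference from Protocol 10.4.1 in SAP 7.9.

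The cost is SAP wording, one extra block of rows and a slightly longer listing. The data are already collected under Protocol 9.2.
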